7.2 MISSING DATE OF THE LAST DOSE OF STUDY DRUG

When the date of the last dose of double-blind study drug is missing for a patient in the Safety Population, all efforts should be made to obtain the date from the Investigator. If after all efforts are made it is still missing, the last eDiary entry date will be used as the last dose date.

7.3 MISSING SEVERITY ASSESSMENT FOR ADVERSE EVENTS

If severity is missing for an AE that started prior to the first dose of double blind study drug, all efforts should be made to obtain the severity from the investigator. If it is still missing after all efforts, then a severity of “Mild” will be assigned. If the severity is missing for an AE that started after the first dose of double-blind study drug, then a severity of “Severe” will be assigned. The imputed values for the missing severity assessment will be used for the incidence summary, while the actual missing values will be presented in data listings.

7.4 MISSING RELATIONSHIP TO STUDY DRUG FOR ADVERSE EVENTS

If the relationship to study drug is missing for an AE that started after the first dose of double-blind study drug, all efforts should be made to obtain the relationship from the investigator. If it is still missing after all efforts, a causality of “Related” will be assigned in the corresponding analysis derived data set. The imputed values for the missing relationship to double-blind study drug will be used only for incidence summary, while the actual missing values will be presented in data listings.

7.5 MISSING DATE INFORMATION FOR ADVERSE EVENTS

The following imputation rules apply to cases in which the start date is incomplete (i.e., partial missing) for adverse events.

a. If AEs occurred during the Screening or Pretreatment Period (i.e., the Screening or Pretreatment Period is checked on the AE eCRF)

Missing day and month

- If the year is the same as the year of the date of informed consent, then the day and month of the date of informed consent will be assigned to the missing fields.
- If the year is prior to the year of the date of informed consent, then December 31 will be assigned to the missing fields.
- If the year is after the year of the date of informed consent, then January 1 will be assigned to the missing fields.

Missing month only

- The day will be treated as missing and both month and day will be replaced according to the above procedure.

Missing day only

- If the month and year are the same as the month and year of the date of informed consent, then the date of informed consent will be assigned to the missing day.
- If either the year is before the year of the date of informed consent or if both years are the same but the month is before the month of the date of informed consent, then the last day of the month will be assigned to the missing day.
- If either the year is after the year of the date of informed consent or if both years are the same but the month is after the month of the date of informed consent, then the first day of the month will be assigned to the missing day.

If the stop date is complete and it is before the date of randomization and the imputed start date as above is after the stop date, the start date will be imputed by the stop date. If the stop date is complete and it is on or after the date of randomization and the imputed start date as above is after the stop date, the start date will be imputed by the date immediately before the date of randomization.

If the start date is completely missing, then the date of informed consent will be used to impute the start date.

b. If AEs occurred during the Treatment Period (i.e., the Treatment Period is checked on the AE eCRF)

Missing day and month

- If the year is the same as the year of the date of the first dose of double-blind study drug, then the day and month of the date of the first dose of double-blind study drug will be assigned to the missing fields.
- If the year is prior to the year of the date of the first dose of double-blind study drug, then December 31 will be assigned to the missing fields.
- If the year is after the year of the date of the first dose of double-blind study drug, then January 1 will be assigned to the missing fields.

Missing month only

- The day will be treated as missing and both month and day will be replaced according to the above procedure.

Missing day only

- If the month and year are the same as the month and year of the date of the first dose of double-blind study drug, then the date of the first dose of double-blind study drug will be assigned to the missing day.
- If either the year is before the year of the date of the first dose of double-blind study drug or if both years are the same but the month is before the month of the date of the first dose of double-blind study drug, then the last day of the month will be assigned to the missing day.
- If either the year is after the year of the date of the first dose of double-blind study drug or if both years are the same but the month is after the month of the date of the first dose of double-blind study drug, then the first day of the month will be assigned to the missing day.

If the stop date is complete and the imputed start date as above is after the stop date, the start date will be imputed by the stop date.

If the start date is completely missing and the stop date is complete, then the following algorithm is used to impute the start date:

- If the stop date is after the date of the first dose of double-blind study drug, the date of the first dose of double-blind study drug will be assigned to the missing start date.
- If the stop date is before the date of the first dose of double-blind study drug, the stop date will be assigned to the missing start date.

7.6 MISSING DATE INFORMATION FOR PRIOR OR CONCOMITANT MEDICATIONS

For prior or concomitant medications, incomplete (i.e., partially missing) start date and/or stop date will be imputed. When the start date and the stop date are both incomplete for a patient, impute the start date first.

7.6.1 Incomplete Start Date

The following rules will be applied to impute the missing numerical fields. If the stop date is complete and the imputed start date is after the stop date, then the start date will be imputed using the stop date.

Missing day and month

- If the year of the incomplete start date is the same as the year of the date of the first dose of double-blind study drug, then the day and month of the date of the first dose will be assigned to the missing fields.
- If the year of the incomplete start date is prior to the year of the date of the first dose of double-blind study drug, then December 31 will be assigned to the missing fields.

Missing month only

- The day will be treated as missing and both month and day will be replaced according to the above procedure.

Missing day only

- If the month and year of the incomplete start date are the same as the month and year of the date of the first dose of double-blind study drug, then the day of the date of the first dose will be assigned to the missing day.
- If either the year is before the year of the date of the first dose of double-blind study drug or if both years are the same but the month is before the month of the date of the first dose of double-blind study drug, then the last day of the month will be assigned to the missing day.

- If either the year is after the year of the date of the first dose of double-blind study drug or if both years are the same but the month is after the month of the date of the first dose of double-blind study drug, then the first day of the month will be assigned to the missing day.

7.6.2 Incomplete Stop Date

The following rules will be applied to impute the missing numerical fields. If the date of the last dose of double-blind study drug is missing, replace it with the last diary entry date. If the imputed stop date is before the start date (imputed or non-imputed start date), then the imputed stop date will be equal to the start date.

Missing day and month

- If the year of the incomplete stop date is prior to the year of the date of the last dose of double-blind study drug, then December 31 will be assigned to the missing fields.

Missing month only

- The day will be treated as missing and both month and day will be replaced according to the above procedure.

Missing day only

- If either the year is before the year of the date of the last dose of double-blind study drug or if both years are the same but the month is before the month of the date of the last dose of double-blind study drug, then the last day of the month will be assigned to the missing day.

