5.8 PRIOR AND CONCOMITANT MEDICATION

Prior medication is defined as any medication taken before the date of the first dose of double-blind study drug. Concomitant medication is defined as any medication taken on or after the date of the first dose of double-blind study drug during the Treatment Period. Medications started after the date of the last dose of double-blind study drug will not be considered concomitant medications.

Both prior and concomitant medications will be coded by drug name and therapeutic class using World Health Organization Drug Dictionary Enhanced (WHO DDE) December 2015. The use of prior and concomitant medications will be summarized for the Safety Population by the number and percentage of patients in each treatment group receiving each medication within each therapeutic class. If a patient took a specific medication multiple times or took multiple medications in the same category (based on Anatomical-Therapeutic-Chemical classification), that patient would be counted only once for the coded drug name or therapeutic class.

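### For one pattern of partial medication dates, SAP 7.6 moves a stop month recorded as before treatment up to Day 1, so the drug is tabulated as concomitant and not prior (minor)

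*SAP*

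**What the plan says.** Six statements in the SAP act together.

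- **Order (7.6).** "When the start date and the stop date are both incomplete for a patient, impute the start date first".
- **Start date (7.6.1).** With day and month missing: "If the year of the incomplete start date is the same as the year of the date of the first dose" of study drug, "then the day and month of the date of the first dose will be assigned to the missing fields". A start that lacks only its month goes the same way: "The day will be treated as missing and both month and day will be replaced according to the above procedure".
- **Safeguard on the start (7.6.1).** A guessed start that falls too late takes the value of the stop ("If the stop date is complete and the imputed start date is after the stop date, then the start date will be imputed using the" …). This requires a complete stop date.
- **Stop date (7.6.2).** If only the day is missing and the month is earlier than that of the last dose, "then the last day of the month will be assigned to the missing day".
- **Override on the stop (7.6.2).** A guessed stop that falls too early takes the value of the start ("If the imputed stop date is before the start date (imputed or non-imputed start date), then the imputed stop date will be equal to" …).
- **Use (5.8).** "Concomitant medication is defined as any medication taken on or after the date of the first dose". A prior medication is one taken before that date. Both kinds are summarised as counts and percentages in the Safety Population.

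**The concern.** In the affected record the stop month is firm information and the start is a guess within a year. SAP 7.6.1 accepts that a complete stop date outranks a guessed start. SAP 7.6.2 reverses that ranking as soon as the stop date lacks its day, even when every day of the recorded month is before first dose.

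This differs from ordinary caution. Counting a drug as concomitant is a sensible default when its timing is unknown, but here the record already excludes use on treatment.

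Such records can arise. Protocol 3.4.8 collects medicines taken in the 30 days before the Screening Visit, which may be as early as Day -49, so recorded stops can lie up to 30 + 49 = 79 days before Day 1. What is at stake is the accuracy of two tables. The concomitant summary could list a drug, possibly one on the prohibited list in Protocol Appendix 4, that the record says had already been stopped, and the prior summary would omit it.

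**Working it through.** The plan gives no figure to reproduce. The check applies the rules literally to records with assumed calendar dates.

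**Worked record.** Assume first dose 15 June 2016 and last dose 10 August 2016. The recorded start is *2016* and the recorded stop is *May 2016*.

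1. Start (7.6.1): same year as first dose, so 15 June 2016. The safeguard does not apply because the stop date is incomplete.
2. Stop (7.6.2): May precedes the last-dose month, so 31 May 2016.
3. Override (7.6.2): 31 May is before 15 June, so the stop becomes 15 June 2016.
4. Class (5.8): the drug starts and stops on Day 1, so it is concomitant and not prior. The record itself puts the stop at least 15 days before first dose (31 May to 15 June).

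**The same drug with other date patterns, same assumed first and last dose:**

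| Recorded start | Recorded stop | Imputed start | Imputed stop | Class |
|---|---|---|---|---|
| 2016 | May 2016 | 15 Jun 2016 | 15 Jun 2016 | concomitant only (wrong) |
| 2016 | 20 May 2016 | 20 May 2016 | 20 May 2016 | prior only |
| Apr 2016 | May 2016 | 30 Apr 2016 | 31 May 2016 | prior only |
| 3 Apr 2016 | May 2016 | 3 Apr 2016 | 31 May 2016 | prior only |
| 2015 | May 2016 | 31 Dec 2015 | 31 May 2016 | prior only |
| 2016 | Jun 2016 | 15 Jun 2016 | 30 Jun 2016 | concomitant only (timing unknown, so reasonable) |

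The first two rows show the inconsistency: both stop dates exclude treatment, yet adding the day changes the class.

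**Enumeration.** For five assumed first-dose dates, take every stop 1 to 79 days before first dose that falls in an earlier calendar month, and every start 0 to 399 days before that stop. Record the start as complete, month-year or year-only, and the stop as complete or month-year. Five of the six combinations gave 0 errors at every first-dose date. The sixth, a year-only start with a month-year stop, gave:

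| First dose | Wrongly concomitant | Records with a start in the first-dose year |
|---|---|---|
| 10 Mar 2016 | 1,830 of 28,000 | stop on days 1 to 60 of the year: 60 × (1 + 60)/2 = 1,830 |
| 15 Jun 2016 | 7,800 of 26,000 | days 88 to 152: 65 × (88 + 152)/2 = 7,800 |
| 20 Sep 2016 | 12,870 of 24,000 | days 185 to 244: 60 × (185 + 244)/2 = 12,870 |
| 10 Dec 2016 | 21,035 of 28,000 | days 266 to 335: 70 × (266 + 335)/2 = 21,035 |
| 20 Jan 2017 | 0 of 24,000 | none: no earlier month in that year |

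The last column uses the fact that a stop on day D of the first-dose year has exactly D of the 400 starts in that year. The counts agree exactly, so all records with the pattern fail and no others do. These are counts on a grid and do not estimate a rate in the trial.

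The override also fires when the start year precedes the first-dose year (start *2015*, stop *May 2015* gives a stop of 31 December 2015). The stop date is then wrong, but the drug is still prior.

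**Size per record.** With about 65 patients per arm (Protocol 3.3), one misplaced patient moves a drug's row by 1/65, about 1.5 percentage points.

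**The case against.** The strongest reply is that this is a narrow corner of a descriptive table. Much of it stands.

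- **Scope.** A reader might infer that any drug known to have stopped before treatment is reported as taken on Day 1. The text does not support that. Complete stop dates, month-year starts and start years before the first-dose year are all classified correctly. A long-standing drug recorded by start year alone will often fall in the last group.
- **Consequence.** A reader might also infer that the rule could make the treatment effect look confounded by prohibited therapy. The primary analysis (SAP 5.10.1), the responder definitions (SAP 5.10.2) and the Per-Protocol Population (SAP 5.2.4) do not use medication dates. Rescue antacid use comes from the eDiary (SAP 5.10.6). Protocol deviations are identified before unblinding (SAP 5.3), and nothing says that imputed medication dates are used for this. The rule also takes no account of treatment arm.
- **Which drugs.** It is tempting to say that washed-out drugs are the most likely to have partial dates. The documents do not say so. Most recent H2RA and antacid use are collected as specific items (Protocol 3.4.8), washout begins at the Screening Visit (Protocol 3.6.1.1), and monitors raise missing data with the investigator (Protocol 5.1). These steps should reduce the number of such records.

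None of this removes the defect. No provision exempts a partial stop date whose whole month precedes first dose, and for internally consistent records the override never corrects a class.

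**Conclusion.** The rule is wrong as written for one pattern: a start date with its month missing in the calendar year of first dose, together with a stop date lacking only its day in a month before the first-dose month. Every such record is counted as concomitant and dropped from the prior summary, against the recorded stop month and against the principle already in SAP 7.6.1.

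Severity is minor. Only the descriptive prior and concomitant medication summaries change, and no efficacy analysis is stated to depend on them. The number of affected records cannot be found from the documents and may be zero; any percentage for the trial would rest on assumed durations of prior use.

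The conclusion assumes that the dates imputed under SAP 7.6 feed the SAP 5.8 classification, as the title of 7.6 implies, and that the recorded year and month are correct. The calendar dates above are illustrations.

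**What to change.** Make three small edits to the SAP before unblinding.

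1. In 7.6, when both dates are incomplete, impute the stop date first.
2. In 7.6.1, extend the safeguard: *If the stop date (complete or imputed) is before the imputed start date, the start date will be set to the stop date.*
3. In 7.6.2, restrict the override to complete (non-imputed) start dates. Do not delete it, because it is the only rule for a partial stop date that falls before a complete start date.

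On the worked record this gives a start and stop of 31 May 2016, so the drug is prior only. A stop in the first-dose month is still treated cautiously as concomitant.

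The cost is a small programming change with no new data collection. Slightly fewer drugs will be counted as concomitant, all of them with a recorded stop month that excludes treatment.

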7.7 CHARACTER VALUES OF CLINICAL LABORATORY PARAMETERS

If the reported value of a clinical laboratory parameter cannot be used in a statistical summary table due to, for example, it being a character string rather than a numerical type, a coded value needs to be appropriately determined and used in the statistical analyses. However, the actual values as reported in the database will be presented in data listings.

[Table 7.7-1](#) shows examples of how some possible laboratory results should be coded for the analysis.

Table 7.7-1. Examples of Coding Special Character Values for Clinical Laboratory Parameters

Laboratory Test, SI Unit	Possible Laboratory Results	Coded Value for Analysis
CHEMISTRY		
ALT, U/L	< 5	0
AST, U/L	< 5	0
Bilirubin, total, µmol/L	< 2	0

ALT = alanine aminotransferase; AST = aspartate aminotransferase; SI = *Le Système International d'Unités* (International System of Units).

7.8 HEALTH OUTCOMES PARAMETERS

7.8.1 Short Form 12 Health Survey Version 2

The SF-12 is a multipurpose, short-form health survey consisting of 12 questions designed for use in clinical practice and research, health policy evaluations, and general population surveys.

For more information, contact the Office of the Vice President for Research and the Office of the Vice President for Student Affairs.

© 2010 by the author; licensee MDPI, Basel, Switzerland. This article is an open access article distributed under the terms and conditions of the Creative Commons Attribution license (<http://creativecommons.org/licenses/by/3.0/>).

For more information, contact the Office of the Vice President for Research and the Office of the Vice President for Student Affairs.

10.1007/s00332-010-9000-0

For more information, contact the Office of the Vice President for Research and Economic Development at [contact] or [contact].

For more information, contact the Office of the Vice President for Research and Economic Development at [contact] or [contact].

© 2019 Pearson Education, Inc.

11. **What is the primary purpose of the *Journal of Clinical Endocrinology and Metabolism*?**

Digitized by [contact]

For more information, contact the Office of the Vice President for Research and Economic Development at [contact] or [contact].

[figure not shown]
For more information, contact the Office of the Vice President for Research and Economic Development at [contact] or [contact].

[figure not shown]
© 2019 Pearson Education, Inc.

© 2013 Pearson Education, Inc. All Rights Reserved. May not be copied, scanned, or duplicated, in whole or in part. Due to electronic rights, some third party content may be suppressed from the eBook and/or eChapter(s). Editorial review has determined that any suppressed content does not materially affect the overall learning experience. Pearson Education, Inc. reserves the right to remove additional content at any time if subsequent rights restrictions require it.

Page 10

[figure not shown]
[REDACTED]

7.8.2 EuroQol-5 dimension (EQ-5D-3L)

The 5-item responses of the EQ-5D-3L define a health state that can be converted into a single summary utility index that assigns weights (ie, value) to each level. Different weights are available. [REDACTED]

[figure not shown]

[figure not shown]

9. APPENDICES

[figure not shown]
APPENDIX I GSRS-SELF

[figure not shown]

[figure not shown]

[figure not shown]

APPENDIX II SF-12V2

APPENDIX III EQ-5D-3L QUESTIONNAIRE
